To estimate the initial effects of GAP, we will use survey, viral load, and monitoring data. We will first examine if randomization succeeded by conducting balance tests with baseline data, which will also inform the specification of the effects estimation model. Second, we will examine loss-to-follow-up (LTF) (expected not to be >10%) and determine if those LTF have different characteristics of those retained and if there is any variation between intervention and control groups. Third, we will estimate initial effects of the intervention. We will first estimate the intention-to-treat (ITT) effect using linear probability (or logistic) model with a GAP intervention indicator as the only explanatory variable and using endline data only. The ITT model will be $Y_i = \alpha_0 + \alpha_1 P_i + \varepsilon_i$, where Y_i is the outcome of individual i , P_i is a dummy indicator variable for being in the treatment group or not, and ε_i is the standard error term. The coefficient α_1 will be our ITT effect estimate. Although the GAP intervention will be randomly allocated across participants, it is possible that some differences in baseline characteristics and outcomes between the groups will be observed. To correct for those imbalances, we will use difference-in-differences (DID) models that include baseline covariates; the DID model estimates intervention effects by taking the difference between the changes observed in the outcome in the intervention group and the changes in the control group, adjusting for baseline differences. The DID model will be estimated using baseline, midline, and endline data and will be specified as: $Y_{it} = \alpha_0 + \alpha_1 P_i + \alpha_2 T1_t + \alpha_3 P_i * T1_t + \alpha_4 T2_t + \alpha_5 P_i * T2_t + \alpha_6 X_i + \varepsilon_{it}$, where Y_{it} is the outcome of individual i at time t , P_i is an indicator variable for being in the intervention group or not, $T1_t$ is an indicator variable for the observation from midline, $T2_t$ is an indicator variable for the observation from endline, X_i represents characteristics of the individual at baseline, and ε_{it} is the standard error term. The coefficient α_3 will be our DID intervention effect at

midline, and α_5 at endline. This DID model allows us to examine the evolution of the intervention effects over time.

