A second set of analyses will examine the effect of each component of the intervention on the main outcome at midline and endline. We will estimate the following model: $Y_i = \alpha_0 + \alpha_1 P1_i + \alpha_2 P2_i + \alpha_3 P3_i + \alpha_4 X_i + \varepsilon_i$ where $P1_i$ is a measure of individual counseling (e.g. # of counseling sessions individual i received); $P2_i$ is a measure of navigation (e.g. # of interactions with individual i); and $P3_i$ is a measure of community support building (e.g. # of group sessions attended by individual i). We will further extend this model to examine if different levels of intensity of exposure have different effects on the outcome. We will define three levels of intensity (low, medium, high) depending on the number of navigation interactions to estimate the following model: $Y_i = \alpha_0 + \alpha_1 P1_i + \alpha_{2Med} P2Med_i + \alpha_{2High} P2High_i + \alpha_3 P3_i + \alpha_4 X_i + \varepsilon_i$ where, $P2Med_i$ is a dummy variable indicating that individual i had medium exposure to navigation and $P2High_i$ is high intensity exposure to navigation sessions. In this model, α_{2Med} is the effect of medium exposure to navigation on the outcome and α_{2High} is the effect of high exposure to navigation on the outcome. The reference category is low exposure.

The minimum detectable effect for a power of 80%, a significant level of 5%, and a 50/50 split of the 120 individuals in the sample between the treatment and control group is of +13.3 percentage points, assuming an expected loss to follow up of 10%, and expected baseline prevalence of viral suppression to be 64%.

10. Data Management and Monitoring

Confidentiality of all study participants will be strictly maintained across all study activities. Interviewers, intervention staff, lab staff, support services staff, and all other relevant project staff will be trained on procedures for maintaining confidentiality. Interviewers assigned to conduct the survey assessments and qualitative interviews and focus groups will be hired by IDCP, which has a longstanding history of conducting confidential and respectful HIV-related research activities with key populations. All study data, laboratory specimens, and forms will be identified by a coded participant ID number only, to maintain participant confidentiality.

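### The DID model chosen to correct chance baseline imbalance over-corrects an imbalance in viral suppression, and its covariate term adds almost nothing; adjusting for baseline suppression does both jobs better

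*Protocol*

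**What the plan says.** Everything here is in section 9 of the protocol (Statistical Considerations). Balance tests come first, "which will also inform the specification of the effects estimation model". Loss to follow-up is then examined, to "determine if those LTF have different characteristics of those retained and if there is any variation between intervention and control groups". The first effect estimate is an unadjusted endline comparison with arm as the only regressor.

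The protocol then grants that "it is possible that some differences in baseline characteristics and outcomes between the groups will be observed", and gives the remedy: "To correct for those imbalances, we will use difference-in-differences (DID) models that include baseline covariates". It describes DID as comparing the change in the intervention group with the "changes in the control group, adjusting for baseline differences". On the data it says: "The DID model will be estimated using baseline, midline, and endline data and will be specified as", and an equation follows. That equation holds arm (P), midline (T1) and endline (T2) indicators, the two arm-by-visit products, and one term alpha_6*X_i, where X_i "represents characteristics of the individual at baseline". The effects are alpha_3 at midline and alpha_5 at endline. The model is also meant to show how the effect evolves over time.

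There are no X-by-visit terms, and baseline suppression is a response, not a regressor. Apart from the unadjusted endline model, section 9 gives no other model for the overall effect of the intervention. It states no correlation between visits.

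**The concern.** DID is called on here because an imbalance may have been seen after randomisation. That imbalance is due to chance, so part of it would be expected to disappear by endline without any treatment effect. A method that subtracts all of it pushes the estimate the other way. The covariates are listed as part of the remedy, yet a term that is constant over visits may have no influence on a contrast of changes. If both points hold, the estimate reported as corrected could carry a sizeable error in exactly the trials where the correction is used, and a pilot with 60 per arm would give up precision that its own data could supply.

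**Working it through.** **Inputs.** From the protocol: 60 per arm (section 4); 64% baseline suppression and 10% loss (section 9: "assuming an expected loss to follow up of 10%, and expected baseline prevalence of viral suppression to be 64" per cent); the printed DID equation. Assumed, because the protocol gives no value: the within-person correlation rho between baseline and endline suppression, taken as 0.33, 0.44, 0.55 and 0.71. The protocol has no figure of its own on this point to reproduce. Its minimum detectable effect of +13.3 points is a separate matter and is not used below.

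**Step 1: the covariate term.** Arm and visit form six saturated cells, so least squares gives

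alpha_5 = [(Ybar_I2 - Ybar_I0) - (Ybar_C2 - Ybar_C0)] - alpha_6 × [(Xbar_I2 - Xbar_I0) - (Xbar_C2 - Xbar_C0)]

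where I and C are the arms, and 0 and 2 are baseline and endline. X_i does not change over time. With complete data, the mean of X in each arm is the same at every visit, the second bracket is zero, and alpha_5 does not depend on X_i. The same holds for alpha_3. I fitted the printed equation to 500 simulated trials with and without X_i: the largest change in either coefficient was 2e-15, also when X_i was baseline suppression itself.

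Four cases follow:
- *Effect of X the same at every visit.* Differencing has already removed the imbalance, so X_i is redundant.
- *Random loss (5% at midline, 10% at endline).* X_i moves alpha_5 by about 0.5 point on average, through the missing rows only.
- *Loss that depends on X differently by arm.* Here X_i helps. With assumed loss of 22% (X=1) and 2% (X=0) in one arm against 3% and 15% in the other, alpha_5 is biased by about -2 points without X_i and about 0 with it.
- *X predicts change.* The imbalance stays. With an assumed 15-point better change when X=1 and prevalence 45% against 35%, the expected bias is 15 × 0.10 = 1.5 points. Simulation with 10% random loss gave 1.4 to 1.5 with X_i in the model.

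**Step 2: imbalance in suppression.** Let d be the observed chance difference at baseline and tau the true effect.
- Unadjusted endline: E(estimate | d) = tau + rho × d
- DID: E(estimate | d) = tau + rho × d - d = tau - (1 - rho) × d
- Endline adjusted for baseline: E(estimate | d) = tau

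With tau = 0 and d = +10 points:

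| rho | DID, formula | DID, simulated slope × 10 | Unadjusted endline, formula |
|---|---|---|---|
| 0.33 | -6.7 | -6.9 | +3.3 |
| 0.44 | -5.6 | -5.5 | +4.4 |
| 0.55 | -4.5 | -4.5 | +5.5 |
| 0.71 | -2.9 | -3.0 | +7.1 |

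The simulated slope for the baseline-adjusted model was about 0 throughout.

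**Step 3: how often.** The SD of d is sqrt(2 × 0.64 × 0.36 / 60) = 0.0876, or 8.8 points. A difference of 10 points is 6 participants out of 60. The exact binomial probability of 6 or more in either direction is 29.5%. The normal approximation without continuity correction gives 25%.

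**Step 4: precision.** Relative to the unadjusted endline variance, DID has factor 2(1 - rho) and the baseline-adjusted model has 1 - rho². DID equals unadjusted endline at rho = 0.5. The ratio DID/adjusted is 2(1 - rho)/(1 - rho²) = 2/(1 + rho), which exceeds 1 for every rho below 1. With 60 per arm and complete data, the SDs in points are:

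| rho | Unadjusted endline | DID | Baseline-adjusted | Variance ratio DID/adjusted |
|---|---|---|---|---|
| 0.33 | 8.8 | 10.1 | 8.3 | 1.50 |
| 0.44 | 8.8 | 9.3 | 7.9 | 1.39 |
| 0.55 | 8.8 | 8.3 | 7.3 | 1.29 |
| 0.71 | 8.8 | 6.7 | 6.2 | 1.17 |

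Simulated SDs agree within 0.1 point: DID 10.2, 9.3, 8.3 and 6.8; adjusted 8.3, 8.0, 7.4 and 6.2; endline about 8.8.

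**The case against.** DID is a valid estimator in a randomised trial. Averaged over randomisations it is unbiased, and it supplements an endline analysis that is untouched. It also does part of its job. For a characteristic with a stable effect, at prevalence 45% against 35%, a simulation gave a bias of about 2 points in the unadjusted endline estimate and under 0.1 point in DID. So a reader should not infer that the model fails to correct imbalance in characteristics, or that X_i is useless: with stable effects it is redundant, and under differential loss it helps. What is left uncorrected, a covariate that predicts change, is small under the assumed values.

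Nor may a reader infer that DID is always worse than no correction. That depends on rho, which the documents do not give. Among simulated trials with an imbalance of at least 10 points, the root mean squared error was 10.9 points for DID against 10.0 for unadjusted endline at rho 0.45, but 9.4 against 10.8 at 0.57 and 7.4 against 11.7 at about 0.7.

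A further tempting step is to fault the standard errors of the three-visit model. Section 9 names no variance estimator, but an analysis plan that is not shown may do so, and no finding is made.

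All of this stands. It does not remove the point: the protocol assigns DID to the situation in which an imbalance has been observed, where the conditional error applies, and the comparison with baseline adjustment favours adjustment whatever rho is below 1.

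**Conclusion.** The point holds as a weakness in the choice of model, not as an invalid analysis. The printed DID model over-corrects a chance imbalance in suppression by (1 - rho) times its size: 3 to 7 points per 10 points of imbalance over the assumed rho of 0.71 to 0.33. Imbalances that large occur in about 30% of trials of this size. Its variance is 1.17 to 1.50 times that of a baseline-adjusted model over the same range. The covariate term has exactly no effect on alpha_3 and alpha_5 in the linear form with complete data, and little under random loss.

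The sizes rest on the assumed rho and on the linear form; the ranking of DID below baseline adjustment rests only on rho being below 1. In a logistic version on complete data, X_i moved the log odds ratio by 0.016 on average, so the result there is approximate. The first-line endline comparison is unaffected. The change is worth making before analysis, mainly because it costs nothing.

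**What to change.** In section 9, for the imbalance-corrected effects, replace alpha_3 and alpha_5 with two models: suppression at midline, and suppression at endline, each on arm, baseline suppression and a few baseline covariates named in advance. Fitting both visits still shows how the effect evolves. Under the differential-loss pattern in the working, the adjusted endline model was also free of bias (0.0 to -0.1 point), so nothing that X_i offered is lost.

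DID can stay as a sensitivity analysis. If it does, adding X-by-T1 and X-by-T2 terms would deal with covariates that predict change, but not with the over-correction of baseline suppression.

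Cost: one or two model lines in section 9. Survey and viral load are already collected at all three visits, so there is no data or enrolment cost.

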3.2 Secondary Objectives

Examine pathways of influence (e.g. decreased stigma, increased cohesion) and experiences with the intervention to identify specific areas for improvement and scale up.

4. Study Design

This is a randomized control trial of the GAP intervention (Gender Affirming *Abriendo Puertas* (Opening Doors)). The GAP intervention includes four components that will be implemented over a 12-month period: 1) individual counseling; 2) peer navigation; 3) provider training and 4) community building. Upon consenting to enter the study, participants will be randomly assigned to the intervention arm (n=60) or the control arm (n=60). The assessment of the GAP intervention will be guided by a mixed methods design, including quantitative surveys, biological assessments, and qualitative interviews.

Both intervention and control participants will complete a baseline socio-behavioral survey and blood draw for viral load testing. These assessments will be repeated at midline (6 months) and endline (12 months). A sub-group of intervention participants (n=20) will be invited to participate in qualitative interviews at baseline, midline, and endline.

Intervention participants will be assigned a navigator upon completing baseline assessments. Navigators will maintain monthly communication (at a minimum) with intervention participants during the 12-month intervention period. Intervention participants will be scheduled for their first individual counseling session within two weeks following enrollment. During the second half of the intervention period (months 6-12), intervention participants will be invited to participate in community building activities hosted at two local trans organizations.

Control group participants will be contacted monthly by a member of the study team to facilitate retention and maintain contact information. They will not receive any other intervention. However, if a control group member attends a community building activity during months 6-12, they will not be turned away.

The study team will facilitate training in gender affirmative care with providers and staff at the HIV clinics where study participants receive care during the 12-month intervention period.

At midline and endline, intervention staff and HIV care providers will be invited to participate in focus groups to document their experiences with the intervention and recommendations for improvement.

5. Study Population

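### The stated minimum detectable effect of +13.3 points does not follow from its inputs: 120 participants with 10% loss can detect about +23 points, and power at +13.3 is about 33%

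*Protocol*

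**What the plan says.** Section 4 fixes the allocation: "participants will be randomly assigned to the intervention arm (n=60) or the control arm (n=60"). The primary objective (Section 3.1) is preliminary efficacy on viral suppression at 12 months, and the primary outcome (Section 7.1) is binary, with a threshold of 400 copies/mL.

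Section 9 plans two effect models. The first is an intention-to-treat comparison with the arm indicator as its only regressor, "using endline data only". The second is a difference-in-differences (DID) model on baseline, midline and endline data with baseline covariates. In that model α_3 is the midline effect and α_5 the endline effect.

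The planning statement closes Section 9. It takes 80% power, a 5% level and equal allocation of 120 people. The smallest difference it claims to detect on those terms "is of +13.3 percentage points, assuming an expected loss to follow up of 10%, and expected baseline prevalence of viral suppression to be 64"%. No sidedness, model, within-person correlation or R² is attached to it.

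**The concern.** The statement reads as a complete two-arm calculation: sample size, split, loss, reference rate, significance level and power are given together. A difference of 13.3 points is small for about 54 people per arm when suppression is near 64%. The 95% confidence interval expected at 64% versus 77.3% would itself extend about 17 points either side.

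This is the only figure in the protocol that says what the trial can detect on its primary outcome. If it is taken at face value, a non-significant result could be read as evidence against effects of 13 points or more. The trial has no such ability, and that reading could count unfairly against the intervention when a larger trial is considered.

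**Working it through.** **Inputs (Section 9 unless noted).** 120 randomised, 60 per arm (also Section 4); 10% loss, so 60 × 0.9 = 54 analysed per arm; reference suppression p₁ = 0.64; 5% significance, taken as two-sided (z = 1.960); 80% power (z = 0.842). The control arm is assumed to stay at 64% at endline.

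**Minimum detectable effect.** The two-proportion test with pooled null variance requires

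d = [1.960·√(2p̄(1−p̄)) + 0.842·√(p₁(1−p₁) + p₂(1−p₂))] / √n, where p₂ = p₁ + d and p̄ = (p₁ + p₂)/2.

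With n = 54 the solution is p₂ = 0.869:
- p̄ = 0.755, so the first root is 0.6085.
- The second root is 0.5864.
- d = (1.960 × 0.6085 + 0.842 × 0.5864)/7.348 = 0.229.

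The result is **22.9 points**, against 13.3 stated (1.7 times larger).

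**Power at +13.3 points (64% to 77.3%).** p̄ = 0.7065, and the two roots are 0.6440 and 0.6371.
- z = (0.133 × √54 − 1.960 × 0.6440)/0.6371 = (0.9773 − 1.2622)/0.6371 = −0.447.
- Power is **32.7%**. Exact enumeration of the chi-square test gives 32.8%. With 60 per arm it is 35.8%.

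**Sample size for +13.3 points.** n = (1.960 × 0.6440 + 0.842 × 0.6371)²/0.133² = 182.8, so **183 analysed per arm**. Dividing by 0.9 gives 204 enrolled per arm (408 in total).

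**Attempts to reproduce 13.3 (detectable difference in points, from 64%).**

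| Calculation | 54 per arm | 60 per arm (no loss) |
|---|---|---|
| Two-sided, pooled | 22.9 | 21.9 |
| Two-sided, unpooled | 22.5 | 21.5 |
| Two-sided, arcsine | 22.7 | 21.7 |
| Two-sided, linear probability, constant variance | 25.9 | 24.6 |
| Two-sided, continuity-corrected | 24.6 | 23.4 |
| One-sided 5%, pooled | 20.7 | 19.8 |
| One-sided 5%, unpooled | 20.4 | 19.5 |

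None comes below 19.5.

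**Could a longitudinal model give it?** For 80% power at 0.133, the sum of the two arms' per-person variances must be at most 54 × (0.133/2.802)² = 0.1217. The unadjusted sum at endline is 0.64 × 0.36 + 0.773 × 0.227 = 0.4059. The variance must therefore fall to 0.1217/0.4059 = 0.300 of its unadjusted value.
- Baseline-adjusted endline: 1 − ρ² = 0.300, so ρ = 0.84 (R² = 0.70).
- Change from baseline (DID): 2(1 − ρ) = 0.300, so ρ = 0.85.
- Other variance conventions give 0.81 to 0.87.

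For binary outcomes there is a ceiling. If an arm moves from 64% to 77.3%, the largest possible baseline-to-endline correlation is √[(0.64 × 0.227)/(0.36 × 0.773)] = 0.72, reached only when nobody in that arm loses suppression. The intervention arm therefore cannot supply 0.84, and the control arm would have to compensate. In this most favourable case the intervention arm's change-score variance is 0.133 × 0.867 = 0.1153. That leaves 0.1217 − 0.1153 = 0.0064 for controls. If control suppression stays at 64%, this variance equals the proportion changing status, and 0.0064 × 54 = 0.3, fewer than one control in 54. The baseline-adjusted version with a common slope allows about 1.5 controls in 54.

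**The case against.** The strongest defence is that Section 9 does not say which model the figure belongs to. The DID model uses three waves and baseline covariates, and a high within-person correlation could yield a smaller figure. If both follow-up waves are averaged, the correlation needed falls to about 0.76 (baseline-adjusted) or 0.80 (DID). A derivation may exist in a document not at hand.

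It stands that the sidedness and model are unstated, so the claim is that 13.3 does not follow from the inputs printed with it. The defence goes no further than that. The first effect analysis uses endline data only. The DID endline effect is α_5, a baseline-to-endline contrast and not an average over waves, and the objective is fixed at 12 months.

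A second objection is that 64% is called a baseline prevalence. Sections 4 and 9, and the description of provider training in Section 6, allow for or concern change over time, and controls may have some exposure to the intervention, so their endline rate could differ. This qualifies the replacement figure without restoring 13.3: with 54 per arm the detectable increase is 21.1 points from 70%, 19.2 from 75% and 17.0 from 80%.

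Third, this is a pilot of preliminary efficacy, and no progression or futility rule is tied to 13.3. That limits the consequence and makes a small sample acceptable. It does not make the stated figure correct.

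**Conclusion.** The stated figure is wrong for the inputs given. For the endline comparison with 54 per arm, two-sided 5% and controls at 64%, the minimum detectable effect is about 23 points, and power at 13.3 points is about 33%, not 80%. The expected 95% interval half-width at 64% versus 77.3% is 1.96 × √(0.4059/54) = 0.170, or 17 points, which is wider than the effect said to be detectable.

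The conclusion does not depend on the choice of formula, sidedness, whether loss is counted, or a control rate up to 80%. Only an unstated longitudinal assumption could change it, and for the 12-month effect the correlation required is above what the intervention arm could show.

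**What to change.** In Section 9, replace +13.3 with about +23 percentage points (64% to 87%). State the basis: 54 analysed per arm, two-sided 5%, 80% power, unadjusted endline comparison, control arm at 64%. Add that power at 13.3 points is about 33%, and that conclusions on preliminary efficacy will rest on the estimate and its 95% confidence interval.

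If 13.3 did come from a longitudinal calculation, the equal alternative is to name the model, the contrast, the sidedness and the assumed correlation, and to show that the correlation is attainable for a binary outcome at these rates.

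Either change costs wording only. The sample size, design and conduct stay as they are; the cost is a less favourable planning figure.
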